4.2 Follow-up Measures

To ensure comprehensive outcome data, follow-up of all children will be conducted through 5 complementary mechanisms, including telephone interviews (**A**), home visits (**B**), hospital surveillance (**C**), investigation of AD incidence up to 2 years of age (**A**, **B**, **D**), and a neurodevelopmental assessment by 5 years of age (**E**).

A) Telephone interviews at age 1 week, 6 weeks, 6 months, 1 year and 2 years of age.

Families will be contacted to assess vital status, hospital admissions, adherence to the recommended routine vaccination schedule (at 6, 10 and 14 weeks), and morbidity. If an infant has died, brief information will be collected regarding the circumstances such as date, location (home or hospital), and symptoms. In prior BHP trials, 99% of families provided at least 1 telephone contact, and >95% successfully provided data on vital status by 6 weeks of age (**Table 1**).[5]

Table 1. BCGSTRAIN II[5] Telephone follow-up data.

Mother supplied telephone number(s) at inclusion	99%
Follow-up success rate (combined for 6-week and 6-month calls)	95%
Successful 6-week follow-up if two phone numbers provided	88%
Successful 6-week follow-up with ≥ three phone numbers provided	97%

This demonstrates the feasibility and minimal loss to follow-up with telephone-based interviews in our setting. Each reported death will be sought separately confirmed by two different follow-up sources (e.g., two separate telephone contacts or one telephone contact and hospital admission outcome data).

B) Cohort of BHP HDSS study area infants: home visit by 2 months and 12 months of age

Approximately 15% (~2,100 with 14,500 inclusions) of the newborns will reside in BHP's Health and Demographic Surveillance System (HDSS) study area. These infants will receive a home visit at 2 and 12 months of age to assess vital status, BCG scar status and morbidity incidence, as done in previous trials.[1,3–5] In addition, the families will be asked about previous symptoms of AD and the infant will be examined for signs of AD. In case AD is suspected, the child will be referred to an AD specialist (see below). For HDSS infants that die, a verbal autopsy will be performed 3-6 months after the death.

C) Hospital admission surveillance

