All admissions to the national hospital's pediatric ward HNSM are monitored and entered daily by a dedicated BHP team.[2,3,47,48] Parental names and telephone numbers are registered for all admissions and will be used for data linkage and data confirmation. Admission charts linked via a unique trial participant vaccination card sticker ID include the diagnosis and admission outcome. For approximately 60% of admitted infants, data from the vaccination card including the unique ID is documented during the admission. To identify remaining admissions not registered with the unique trial ID, a previously validated standardized probabilistic record matching protocol will be applied.[2,3,5] All admissions will be manually vetted by a blinded senior researcher. To assess the likely cause of death or admission, we will use both hospital data, telephone follow-up data, and verbal autopsy data from the BHP study area.

D) Assessment of AD

At the telephone contacts and HDSS home visits, we will ask the mother whether the child has an itchy rash. If the caregiver reports that the child has scratched repeatedly and/or experienced sleep disturbances due to itching and the family resides in the greater metropolitan area of Bissau, a home visit will be offered by a physician experienced in diagnosing AD at a time point where the child suffers from the rash.

At the home visit, the physician will perform a clinical examination to assess whether the child has AD or another condition. Appropriate treatment will be initiated, and guidance will be given for clinical follow-up. At follow-up visits, it will be ascertained if the treatment has helped, and/or if further/other treatment is needed. The data on 1) self-reported AD symptoms and 2) physician-diagnosed AD will be reported separately for the AD outcome.

E) Neurodevelopmental assessment

A subgroup of 500 BHP HDSS children will receive a neurodevelopmental assessment at 5 years of age, provided renewed informed consent. The evaluation will take place at the local health center.

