4.3 Primary and Secondary Outcome Measures

Primary outcome: Mortality and morbidity

The composite outcome of all-cause mortality or first non-fatal admission with infection from randomization to 42 days of age (before the next routine vaccination) in the group given HBV0 compared with the control group.

Secondary outcomes: Neurodevelopmental disorders and AD

AD by 2 years of age

In a subgroup followed to 2 years of age (see sample size calculation): cumulative incidence of AD symptoms (self-reported at home visits or telephone follow-up) and cumulative incidence of AD diagnosed by an MD with special training.

Neurodevelopment by 5 years of age

In a subgroup of 500 singleton children from the HDSS followed to 5 years of age: cognitive outcomes assessed by the Mullen Scales of Early Learning and the Kaufman Assessment Battery for Children. These tests have been tested for validity in Sub-Saharan African children.[49–52]

The outcomes will be further explored to assess the effect by subcategory of outcome and by age (**Table 2**).

Table 2. Trial outcomes and data sources

Primary outcome	Whom	Age assessed	Data source(s)
Composite outcome: all-cause mortality and admission due to non-fatal infection	All infants	6 weeks	A, B, C
Secondary outcomes			
I: Self-reported AD and II: physician-diagnosed AD	I: All infants. II: To 200 cases among controls*	2 years	A, B, D
Neurodevelopmental outcomes	500 HDSS children*	5 years	E
Outcome subcategories and by age			
Composite outcome: all-cause mortality and admission due to non-fatal infection	All infants	2 years	A, B, C
All-cause mortality	All infants	6 weeks, 2 years	A, B, C
In-hospital case-fatality (all-cause, infectious diseases)	Hospitalized infants	6 weeks, 2 years	C
Hospital admission for major diseases groups (neonatal conditions aside from sepsis, respiratory infections, bronchitis, diarrheal diseases, malaria, malnutrition-related diseases)	All infants	6 weeks, 2 years	C

* See sample size calculation section below for further information.

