7 ADVERSE EVENTS

BCG can cause axillary lymphadenitis, and very rarely this can ulcerate. Very rarely, in an infant with severe immunodeficiency, BCG can cause disseminated infection (*BCGitis*). OPV can cause vaccine-associated paralytic poliomyelitis diarrhea, fatigue and muscle weakness. For HBV0, the most common reactions are mild soreness, erythema, induration, fatigue, fever, malaise, and influenza-like symptoms. Less common systemic reactions include nausea, vomiting, diarrhea, abdominal pain, abnormal liver function tests, arthralgia, myalgia, rash, pruritus, urticaria.[58] All the listed adverse events are rare or very rare. All three vaccines can cause allergic reactions in very rare circumstances. Each inclusion team will have adrenalin available along with guidelines for medical therapy to handle an acute anaphylactic reaction. All adverse events are captured through the outcome data collection.

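### Self-reported atopic dermatitis has no lower age limit, so itchy rashes that are HBV0 reactions, reported at the age 1-week call, can enter it in excess in the HBV0 arm

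*Protocol*

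**What the plan says.** All places are in the protocol.

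- **When the question is put.** Section 4.2 D: "At the telephone contacts and HDSS home visits, we will ask the mother whether the child has an itchy rash". Section 4.2 A gives the calls: "Telephone interviews at age 1 week, 6 weeks, 6 months, 1 year and 2 years of age". No call is exempted.
- **The outcome.** Section 4.3 defines the first AD measure as "cumulative incidence of AD symptoms (self-reported at home visits or telephone follow-up". Table 2 takes it in all infants to age 2 years, and section 8.2 analyses it as a risk ratio by binomial regression.
- **Symptom filter.** "If the caregiver reports that the child has scratched repeatedly and/or experienced sleep disturbances due to itching", and the family lives in greater Bissau, a physician visit is offered. The filter is tied to that offer, not to the self-reported outcome.
- **Second measure.** At the visit "the physician will perform a clinical examination to assess whether the child has AD or another condition". Then: "The data on 1) self-reported AD symptoms and 2) physician-diagnosed AD will be reported separately for the AD outcome".
- **Known reactions to HBV0.** Section 7: "Less common systemic reactions include nausea, vomiting, diarrhea, abdominal pain, abnormal liver function tests, arthralgia, myalgia, rash, pruritus, urticaria". It adds: "All the listed adverse events are rare or very rare". It gives no rates, and says adverse events are picked up through the outcome data.
- **Setting.** Section 4.1 provides no placebo, section 6.4 has the mother told the allocation, and section 6.2.2 allows enrolment up to 7 completed days of age.

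**The concern.** The 1-week call is the contact closest to vaccination, and the question asked there describes a listed reaction to the intervention. Only one arm receives that intervention, and the person answering knows which arm the child is in. Because the outcome is cumulative to 2 years and the text sets no minimum age, duration, recurrence or post-vaccination window, nothing in the protocol keeps a 1-week report out of it. The HDSS home visits (section 4.2 B) also ask about past AD symptoms, so an early rash could enter later by recall.

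An excess of this kind pushes the risk ratio upward, toward the conclusion that HBV0 raises the risk of AD, which is a concern the trial was set up to test. Randomisation does not remove it, because the error lies in what the question measures. Self-reported AD is also the only AD measure that Table 2 takes in all infants.

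**Working it through.** **Step 1: the plan's own AD figures.** Section 4.4 states that 200 diagnosed control cases allow detection of 256 or 150 cases in the HBV0 arm. At its assumed 10% incidence, 200 cases imply about 2,000 children per arm. With a two-sided 5% test (assumed, as for the primary outcome), pooled variance under the null and no continuity correction, power is 79.6% for 10% vs 12.8% and 79.9% for 10% vs 7.5%. The figures reproduce at 80% power. They concern the physician-diagnosed measure.

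**Step 2: timing.** Enrolment runs from birth to 7 completed days, and vaccination is at enrolment. A call at age 7 days therefore falls 0 to 7 days after HBV0.

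**Step 3: effect on the self-reported risk ratio.**

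Inputs:
- control incidence p = 10%, giving 725 of 7,250 (section 4.4);
- n = 7,250 per arm (section 4.4; all infants, Table 2);
- true risk ratio 1.00 (assumption);
- r = excess proportion of HBV0 infants whose reaction is counted as AD symptoms (assumption, since the documents give no rate). A fraction p of these infants is assumed to become cases anyway.

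Formulas:
- HBV0-arm risk = p + (1 − p)r
- extra cases = n(1 − p)r
- risk ratio = 1 + (1 − p)r/p
- rejection probability from the two-sided two-proportion test, both tails.

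Example, r = 1%: risk = 0.10 + 0.9 × 0.01 = 0.109. Extra cases = 7,250 × 0.009 = 65. Risk ratio = 1.09. Standard error = √[(0.10 × 0.90 + 0.109 × 0.891)/7,250] = 0.00508, so z = 0.009/0.00508 = 1.77 and the rejection probability is about 42.5%.

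| Assumed excess r | Extra cases | Risk ratio | Chance of a significant result |
|---|---|---|---|
| 0.01% | 0.7 | 1.001 | 5.0% |
| 0.1% | 6.5 | 1.009 | 5.4% |
| 0.5% | 33 | 1.045 | 14.5% |
| 1% | 65 | 1.09 | 42.5% |
| 2% | 131 | 1.18 | 94% |

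For scale, the risk ratio detectable with 80% power at this size is about 1.144. To produce that alone, r would have to be 0.1 × 0.144/0.9 = 1.6%.

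**Step 4: sensitivity to the assumptions.**
- Larger trial, 12,500 per arm (the ceiling in section 6.8): r = 0.5% gives about 22% and r = 1% about 64%.
- Lower control risk, 5%, at 7,250 per arm: r = 0.5% gives a risk ratio of 1.095 (25%) and r = 1% gives 1.19 (71%).
- Higher control risk, at 7,250 per arm with r = 1%: 20% gives 1.04 (22%) and 30% gives 1.02 (15%).
- Smaller analysis set. The text of section 4.3 places the AD outcomes in a subgroup, unlike Table 2. With about 2,000 per arm, 10% control risk and r = 1%, the risk ratio is still 1.09. The standard error is 0.00508 × √(7,250/2,000) = 0.00967, so z = 0.93 and the rejection probability is about 15%.

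If early reports are not counted, the part of r that comes only from the 1-week call becomes 0.

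**The case against.** **The case rule.** A reader might infer that one positive answer at the 1-week call makes a child an AD case for good. The protocol does not say so. It gives a question and an outcome described as AD symptoms, without stating which answers make a case. Section 8.2 provides for a separate statistical analysis plan, which is not shown and may set that rule. This stands, and limits the claim to what can enter the outcome. It does not remove the point. An analysis plan can drop the 1-week answers, but it cannot recover the onset or duration of a rash recalled later if neither was recorded.

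**Whether the question is asked at 1 week.** The call content in section 4.2 A is generic and includes vaccines due at 6 to 14 weeks, which cannot be asked about at 1 week. The question is also in the present tense, so a rash that has gone may be missed. This is fair, but section 4.2 D ties the question to the telephone contacts without exception.

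**Size.** A reader might infer a large risk of a false positive from the 1% and 2% rows. Section 7 calls these reactions rare or very rare, and at 0.1% or below the bias is negligible. This stands. A loosely defined symptom measure would probably also have a control incidence above 10%, which shrinks the ratio further.

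**One arm only.** A reader might infer that such rashes occur only after HBV0. Section 7 says all three vaccines can, very rarely, cause allergic reactions, and both arms receive BCG and OPV. Unrelated early rashes in both arms pull the ratio toward 1. The supported wording is an excess in the HBV0 arm.

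**Physician diagnosis.** The examination separates AD from other conditions, so that outcome is largely protected and the point concerns self-report alone.

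**Conclusion.** The point holds for self-reported AD, as a possible one-directional misclassification of unknown and probably small size. The mechanism follows from the protocol's own text: contacts from age 1 week, an itchy-rash question at the contacts, a cumulative outcome without a lower age limit, listed HBV0 reactions that look the same, no placebo, and an unblinded reporter.

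The size rests on an assumed excess that the documents do not supply. With 10% control incidence, 7,250 per arm and no true effect, it is immaterial at 0.1% and starts to matter at about 0.5% to 1%. The documents do not support saying that vaccine reactions will be counted as AD, or that a false positive is likely. Maternal awareness of allocation could add to the excess, but it acts at every call to 2 years and is a separate problem. The change is worth making because it is cheap and removes an error whose direction is known.

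**What to change.** In sections 4.2 D and 4.3 and in Table 2, count self-reported AD only from symptoms reported at or after the 6-week contact and not confined to the first week after vaccination. The second condition also covers early rashes recalled at later contacts, and it needs onset and persistence to be asked there. Keep the rash question at the 1-week call, and report its answers by arm as reactions. Optionally, add a sensitivity analysis that uses reports from the 6-month call onward only.

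The cost is about one sentence in the outcome definition, a brief item on onset and persistence if the forms lack one, and one extra table. The downside is that a few true, very early cases would be dated later, or missed if they resolve before the 6-week contact. The change does not remove bias from unblinded reporting at later calls, and the trial report should say so.

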4.3 Primary and Secondary Outcome Measures

Primary outcome: Mortality and morbidity

The composite outcome of all-cause mortality or first non-fatal admission with infection from randomization to 42 days of age (before the next routine vaccination) in the group given HBV0 compared with the control group.

Secondary outcomes: Neurodevelopmental disorders and AD

AD by 2 years of age

In a subgroup followed to 2 years of age (see sample size calculation): cumulative incidence of AD symptoms (self-reported at home visits or telephone follow-up) and cumulative incidence of AD diagnosed by an MD with special training.

Neurodevelopment by 5 years of age

In a subgroup of 500 singleton children from the HDSS followed to 5 years of age: cognitive outcomes assessed by the Mullen Scales of Early Learning and the Kaufman Assessment Battery for Children. These tests have been tested for validity in Sub-Saharan African children.[49–52]

The outcomes will be further explored to assess the effect by subcategory of outcome and by age (**Table 2**).

Table 2. Trial outcomes and data sources

Primary outcome	Whom	Age assessed	Data source(s)
Composite outcome: all-cause mortality and admission due to non-fatal infection	All infants	6 weeks	A, B, C
Secondary outcomes			
I: Self-reported AD and II: physician-diagnosed AD	I: All infants. II: To 200 cases among controls*	2 years	A, B, D
Neurodevelopmental outcomes	500 HDSS children*	5 years	E
Outcome subcategories and by age			
Composite outcome: all-cause mortality and admission due to non-fatal infection	All infants	2 years	A, B, C
All-cause mortality	All infants	6 weeks, 2 years	A, B, C
In-hospital case-fatality (all-cause, infectious diseases)	Hospitalized infants	6 weeks, 2 years	C
Hospital admission for major diseases groups (neonatal conditions aside from sepsis, respiratory infections, bronchitis, diarrheal diseases, malaria, malnutrition-related diseases)	All infants	6 weeks, 2 years	C

* See sample size calculation section below for further information.

4.4 Number of Subjects (Sample Size)

Based on a recently completed trial of BCG-Denmark+OPV0 vs BCG-Bulgaria+OPV0[6], conducted with the proposed setup and follow-up methodology, we anticipate a 6-week mortality rate of 1.4% and a non-fatal infectious disease admission rate of 2.6%, for a composite risk of 4% in the control group. The number of dropouts in previous trials has been low, and the composite risk of 4% is based on the collected data in the most recent trial[6], e.g., the rate accounts for loss to follow-up. If the rate of the composite outcome of all-cause mortality and non-fatal hospital admission with infection is 4% (0.04) in the control group, and HBV0 increases the rate of the composite outcome by 25% (to $1.25 \times 0.04 = 0.05$) or decreases the rate by 22% (to $0.78 \times 0.04 = 0.0312$), to have 80% power to detect such changes for the primary outcome, with alpha error <0.05, the required sample size is 14,368 newborns, 7,184 in each group, from sampsi .050 .040, a(0.05) p(0.80) and sampsi .040 .0312, a(0.05) p(0.80) in Stata/BE version 18.0. For simplicity, enrolling 14,500 newborns is expected to be possible before HBV0 is introduced in Guinea-Bissau. With a composite outcome prevalence of 4% (0.04), the number of deaths and non-fatal infectious disease admission expected is $7,250 \times 0.04 = 290$. With 290 events in the control group, expected to be reached when 7,250 newborns have been recruited in each trial arm, the trial has 80% power to detect if HBV0 has a beneficial non-specific effect, decreasing the rate of the primary outcome by $\geq 22\%$ or a detrimental non-specific effect, increasing the rate by $\geq 24\%$. This design ensures statistical power and precision to detect also minor NSEs of HBV0, with no known disadvantages to participants. The exact timepoint that the trial will end is determined by the time when the Ministry of Health introduces HBV0 in Guinea-Bissau. We will therefore continue the trial until HBV0 is introduced in Guinea-Bissau or when 25,000 neonates have been enrolled in the trial, whichever comes first. If 25,000 neonates are enrolled in the trial, we will be able to detect an increase in the rate of the composite outcome of 18% and a decrease of 17%.

For AD, little is known about the prevalence in Sub-Saharan Africa, but the available data indicate prevalence rates similar to European Union countries, e.g., approx. 12% among 5-year old children.[53] If the cumulative incidence by 2 years of age is 10%, there would be 725 cases of AD in the control group if we recruit 7,250 children in each arm of the trial. We aim to conduct home visits to identify cases of AD until 200 cases have been diagnosed among controls, which would provide power to detect a 28% increase (to 256 intervention group cases) in the risk of AD for children who receive HBV0 and a 25% decrease (to 150 intervention group cases).

For cognitive outcomes, a sample size of 500 will make this study a large study with power to detect clinically meaningful differences in cognitive abilities between children who did or did not receive HBV0.[49]

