6.4 Blinding Arrangements

Since there is no placebo vaccine, the inclusion teams at each inclusion center will not be blinded to the randomization allocation and the mother/guardian will be informed of the randomization allocation. However, all outcome assessors involved in follow-up procedures will be blinded, ensuring objective outcome assessment while maintaining operational feasibility in the setting. The senior trial statistician, who will conduct the final analysis of the trial data, will be blinded to the randomization allocation until the DSMB decides to unblind the trial.

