The cumulative incidence of atopic dermatitis will be separately investigated for self-reported cases and physician-diagnosed cases using binomial regression providing RRs, also using the Stata cluster command.

All analyses will be done overall and by sex using Stata software (StataCorp, College Station, Texas), with all estimates reported with 95% confidence intervals.

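### Physician-diagnosed AD is defined as a 2-year cumulative incidence, but its home visits end at the 200th control case and no cohort followed to age 2 is defined.

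*Protocol*

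**What the plan says.** Protocol section 4.3 defines both AD measures with the words "In a subgroup followed to 2 years of age (see sample size calculation): cumulative incidence of AD symptoms", followed by AD diagnosed by a specially trained doctor. The section it points to, 4.4, names no subgroup. It gives the expectation "If the cumulative incidence by 2 years of age is 10%, there would be 725 cases of AD in the control group" (7,250 children per arm) and then a rule for ending ascertainment: "We aim to conduct home visits to identify cases of AD until 200 cases have been diagnosed among controls". It claims power for a 28% increase (256 intervention cases) or a 25% decrease (150).

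Table 2 repeats the rule under the heading for whom the outcome covers, "I: All infants. II: To 200 cases among controls", with age 2 years as the age assessed. Section 4.2 (D) offers the physician visit to any child with qualifying itch whose family lives in greater Bissau, with no enrolment cut-off. Section 4.5 says AD follow-up goes on to age 2, and Table 3 shows AD assessment running through 2029.

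Section 8.2 states the analysis: "The cumulative incidence of atopic dermatitis will be separately investigated for self-reported cases and physician-diagnosed cases using binomial regression providing RRs". Section 6.4 blinds the outcome assessors and says that the senior statistician "will be blinded to the randomization allocation until the DSMB decides to unblind the trial". Section 1.2.3 makes the six-monthly DSMB reports blinded.

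**The concern.** A cumulative incidence by age 2 needs every child in the denominator to be under ascertainment until age 2, or an analysis that allows for those who are not. Enrolment is staggered over 1.5 to 2 years, while visits end on one calendar date, set by a case count in one arm. Each child's time under physician ascertainment then depends on the date of enrolment, and binomial regression treats all of it alike. Visits that were never made cannot be recovered by a later analysis plan.

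Two lesser problems follow from the same text. A count among controls requires knowledge of true allocation as cases accrue. And section 4.3 restricts self-reported AD to the subgroup, while Table 2 gives it to all infants.

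**Working it through.** **Inputs from the protocol.** 7,250 controls and 10% AD by age 2 (4.4); enrolment over 18 to 24 months (4.5); stop at 200 control cases (4.4, Table 2); telephone contacts at 1 week, 6 weeks, 6, 12 and 24 months (4.2).

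**Assumptions not in the protocol.** Uniform enrolment. Onset linear in age, front-loaded (70% of cases in year 1) or back-loaded (30% in year 1). Detection continuous or only at the telephone contacts. Share of true cases confirmed by a physician from 100% down to 30%.

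**1. The plan's own figures.** 7,250 × 0.10 = 725 control cases, as stated. The rule therefore stops at 200/725 = 28% of them.

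The power claim can be reproduced with n = 200/0.10 = 2,000 per arm, two-sided alpha 0.05 (no power level is stated for AD; 80% is assumed):

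power = Φ{[|p1 − p2|√n − 1.96√(2p̄(1 − p̄))] / √[p1(1 − p1) + p2(1 − p2)]}

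With p1 = 0.100, p2 = 0.128, p̄ = 0.114: (1.252 − 0.881)/0.449 = 0.827, so power is 79.6%. For 0.100 against 0.075 it is 79.9%. The stated effects thus fit about 2,000 children per arm with complete 2-year risk.

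**2. When the 200th control case falls.** With linear onset, continuous detection and full confirmation, expected control cases at month t during enrolment are λ × (0.10/24) × t²/2, where λ is controls enrolled per month. Setting this to 200 gives t = √(9,600/(0.10λ)).

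- 18 months of enrolment: λ = 7,250/18 = 402.8, so t = 15.4 months. About 6,220 controls are enrolled, with mean age 7.7 months.
- 24 months of enrolment: λ = 7,250/24 = 302.1, so t = 17.8 months. About 5,390 controls are enrolled, with mean age 8.9 months.

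No child has turned 2 in either case. Over all onset and detection patterns, solved numerically:

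| Share of cases confirmed | Month of 200th control case | Enrolled controls past age 2 |
|---|---|---|
| 100% | 13 to 26 | 0 to 8% |
| 75% | 15 to 28 | 0 to 18% |
| 50% | 19 to 33 | 0 to 39% |
| 33% | 27 to 42 | 17 to 77% |
| 30% | 31 to 45 | 40 to 89% |

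Below 200/725 = 28% confirmation, 7,250 controls would not yield 200 cases and the rule would not bite. At full confirmation the crude control proportion at the stop is between 200/7,250 = 2.8% and 200/4,620 = 4.3%, against the 10% assumed by age 2.

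**3. Power at the stop.** The same counts now sit on a larger denominator. With 7,250 per arm, 200 against 256 gives 76.0% and 200 against 150 gives 77.2%. With about 5,250 per arm the figures are 76.5% and 77.6%. The loss is about 2 to 4 points.

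**4. Blinding.** Counts under coded arm labels do not tell which arm is control, so the rule needs someone holding the true allocation. If the total over both arms is T when visits stop, the intervention count is T − 200, which anyone who knows T can work out.

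**The case against.** The strongest reply is that a fixed cohort was meant. Section 4.3 speaks of a subgroup followed to age 2, section 4.5 continues AD follow-up to that age, Table 3 allows for it, and the power figures fit about 2,000 per arm with complete follow-up. That is a plausible intent. But no such cohort is defined anywhere, section 4.2 (D) sets no cut-off, and Table 3 could reflect self-report alone. The passages need to be reconciled.

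Second, a reader might infer that almost no child would reach age 2 under ascertainment. The documents do not support that in general. The 10% is an incidence, not a confirmed yield. A physician diagnosis requires a caregiver report of scratching or disturbed sleep, residence in greater Bissau, acceptance of the visit, and a rash present at the time. At 33% confirmation, 17 to 77% of controls would be past age 2. What stands is that in every scenario tabulated, visits stop before all children get there.

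Third, a reader might infer that the rule forces allocation open to the assessors. It does not. Allocation is on the inclusion form, and an unblinded data role could keep the count. The gap is that no such role is named and that the stop itself reveals the intervention count by subtraction.

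Fourth, the harm is bounded. Allocation is 1:1 in blocks of 24 stratified by sex and place (6.3), this is one of two measures of a secondary outcome, and Table 2 keeps self-reported AD in all infants. All of that stands.

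**Conclusion.** The point holds and should be fixed. Followed as written, the rule does not deliver a 2-year risk of physician-diagnosed AD. At full confirmation, 0 to 8% of enrolled controls have passed age 2 when visits end. At lower confirmation the share is larger but still incomplete, until confirmation is so low that 200 cases are never reached. The ranges rest on assumed onset, uniform enrolment and an unknown confirmed share.

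A biased risk ratio is a tempting further inference, but observation time is balanced between arms by randomisation and nothing in the documents points to a direction. The cost lies in what the estimate means, in a power loss of a few points, and in an unassigned allocation-aware count. The conflict over who contributes to self-reported AD is real but a matter of wording.

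**What to change.** - Replace the stopping rule in section 4.4 and Table 2 with a fixed cohort: the first N enrolled infants living in greater Bissau, both arms, all kept under visit ascertainment to the second birthday.
- Set N on the expected confirmed yield. About 2,000 per arm suffices if the confirmed 2-year risk is 10%. At 50% confirmation, 2,000 per arm would give only 100 control cases and about 48% power for a 28% increase; about 4,000 per arm (200/0.05) would restore 200 control cases. These children are being enrolled anyway. Allow N to be adjusted on the pooled, blinded case rate.
- State any case target as a count pooled over arms, so that nobody needs allocation to apply it.
- Keep binomial regression if follow-up to age 2 is complete. If any child's ascertainment ends earlier, use a time-to-event analysis on the age scale.
- Make section 4.3 and Table 2 agree on whether self-reported AD covers all infants.

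The cost is protocol wording, plus visits that continue until the last cohort child turns 2. For 2,000 per arm, enrolment takes 2,000/7,250 × 18 to 24 = 5.0 to 6.6 months if all live in greater Bissau, so visits end at about months 29 to 31, within Table 3. A larger N or a residence restriction that excludes many children pushes this later.
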